2.4.4.4 Multiplicity issues

To control the family-wise type I error, a hierarchical testing procedure will be applied.

Once the primary variable (change from Baseline to Week 26 in HbA1c) is statistically significant at $\alpha=0.05$ (2-sided), a hierarchical testing procedure will be performed to test the following secondary efficacy variables in the following prioritized order. The testing will stop as soon as an endpoint is found not to be statistically significant at $\alpha=0.05$ (2-sided).

- Comparing sotagliflozin 200 mg versus placebo in change from Baseline to Week 26 in HbA1c
- Comparing sotagliflozin 400 mg versus placebo
 - Change from Baseline to Week 26 in FPG
 - Change from Baseline to Week 26 in body weight
 - Change from Baseline to Week 12 in SBP for patients with baseline SBP ≥ 130 mmHg
 - Change from Baseline to Week 12 in SBP for all patients
 - Proportion of patients with HbA1c $< 7.0\%$ at Week 26
- Comparing sotagliflozin 200 mg versus placebo
 - Change from Baseline to Week 26 in FPG
 - Change from Baseline to Week 26 in body weight
 - Change from Baseline to Week 12 in SBP for patients with baseline SBP ≥ 130 mmHg

Once the above secondary variables are statistically significant at $\alpha = 0.05$ (2-sided), Hochberg's step-up procedure (1) will be performed to test the remaining 4 secondary variables: order a number of m ($m=4$ here) tests by p-values (from lowest to highest) $P_{(1)} \dots, P_{(m)}$ associated with tests $H_{(1)} \dots, H_{(m)}$, find the largest k (called R) so that $P_{(k)} \leq \alpha / (m+1-k)$, conclude $H_{(1)} \dots, H_{(R)}$ statistically significant.

- Percentage change in UACR from Baseline to Week 26 for patients with UACR >30 mg/g at Baseline, comparing sotagliflozin 400 mg and 200 mg, respectively, versus placebo
- Proportion of patients with HbA1c <7.0% at Week 26, comparing sotagliflozin 200 mg versus placebo
- Change from Baseline to Week 12 in SBP for all patients comparing sotagliflozin 200 mg versus placebo.

No multiplicity adjustment will be made on other secondary efficacy variables than mentioned above.

In addition, no further multiplicity adjustment (split of alpha) is needed for multiple analyses (ie, first step and second step analyses [Section 3](#)). The results of the first step analysis will not be used to change the conduct of the ongoing study in any aspect and all primary and secondary efficacy endpoints will be fully evaluable at the time of the first step analysis. Analyses beyond Week 26 will be descriptive.

2.4.5 Analyses of safety data

The summary of safety results will be presented by treatment group. The safety data will be summarized for the 26-week core treatment period and the 52-week entire treatment period separately, unless otherwise specified.

The “observation period” defined in [Section 2.1.4](#) is applicable in all safety analyses for the classification of AEs, determination of treatment-emergent PCSA values and the last on-treatment value for the laboratory, vital sign and ECG.

General common rules

All safety analyses will be performed on the safety population as defined in [Section 2.3.2](#), unless otherwise specified, using the following common rules:

- Safety data in patients who do not belong to the safety population (eg, exposed but not randomized) will be listed separately
- The baseline value (with the exception of serum creatinine and eGFR) is defined as the last available value before the first dose of double-blind IMP. For serum creatinine and eGFR, the baseline value is defined as the average of all values before the first dose of double-blind IMP.
- PCSA values are defined as abnormal values considered medically important by the Sponsor according to predefined criteria/thresholds based on literature review and defined by the Sponsor for clinical laboratory tests, vital signs, and ECG ([Appendix B](#))
- PCSA criteria will determine which patients had at least 1 PCSA during the treatment-emergent adverse event period, taking into account all evaluations performed during the treatment-emergent adverse event period, including nonscheduled or repeated evaluations.

The number of all such patients will be the numerator for the treatment-emergent PCSA percentage.

- The treatment-emergent PCSA denominator by group for a given parameter will be based on the number of patients assessed for that given parameter in the treatment-emergent adverse event period by treatment group on the safety population.
- For laboratory parameters cited in the protocol as efficacy endpoints (including HbA1c and plasma glucose etc), PCSA summaries will not be provided. These parameters will be summarized in efficacy [Section 2.4.4](#).
- For quantitative safety parameters based on central laboratory/reading measurements, descriptive statistics will be used to summarize results and change from baseline values by visit and treatment group for the 52-week entire treatment period only. Summaries will include the last on-treatment value. The last on-treatment value is commonly defined as the value collected at the same day/time of the last administration of IMP for the 52-week entire treatment period. If this value is missing, this last on-treatment value will be the closest value prior to the last administration of IMP during the 52-week entire treatment period.
- The analysis of the safety variables will be essentially descriptive and no systematic testing is planned. Relative risks versus placebo and their 95% CIs may be provided, if relevant.
- Selected safety analyses will be summarized by age, gender, racial subgroups, and other pertinent subgroups (see details in [Section 2.4.5.1](#) and [Section 2.5.2](#)).

2.4.5.1 Analyses of hypoglycemia

Analyses of hypoglycemia will be performed on the TEAE period as defined in Section 2.1.4. Hypoglycemia will be classified as severe hypoglycemia, documented symptomatic hypoglycemia, asymptomatic hypoglycemia, probable symptomatic hypoglycemia or relative hypoglycemia (see Section 2.1.4).

The number (%) of patients with any hypoglycemia, severe hypoglycemia, and documented symptomatic hypoglycemia will be summarized respectively by treatment group during the TEAE period, as well as the incidence rate in patient years. Two types of incidence rates will be presented: the number of patients with at least 1 event per 100 patient-years (calculated as the number of patients with at least 1 event / total exposure in 100 patient-years), and the number of events per 100 patient-years (calculated as the total number of events / total exposure in 100 patient-years). Note: here exposure in days is duration of treatment-emergent AE period, ie, duration of IMP treatment in days +1 (Section 2.1.4).

- The summary of frequency and incidence rate in patient years for severe hypoglycemia or documented symptomatic hypoglycemia will be provided as appropriate by gender (Male, Female), age group (<50, ≥50 to <65, ≥65 years), race (White, Black or African American, Asian, Other) and prior antidiabetic medication (no antidiabetic therapy, insulin, non-insulin).

- A KM curve will also be provided by treatment group for the time to first severe hypoglycemia or documented symptomatic hypoglycemia during the TEAE period for the 52-week entire treatment period only (see Section 2.5.4).

Documented symptomatic hypoglycemia may be presented by ≤ 3.9 mmol/L (≤ 70 mg/dL) and < 3.0 mmol/L (< 54 mg/dL) respectively, as appropriate.

A listing of patients for all events reported on the dedicated e-CRF “Hypoglycemic event information” page will be provided with each category flagged (ie, severe hypoglycemia, documented symptomatic hypoglycemia, asymptomatic hypoglycemia, probable symptomatic hypoglycemia and relative hypoglycemia).

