**Table 1 - Summary of investigational medicinal products during treatment period**

IMP:	Sotagliflozin (200 mg group)	Sotagliflozin (400 mg group)	Placebo group
Name of the IMPs	Sotagliflozin (SAR439954)	Sotagliflozin (SAR439954)	Placebo
Pharmaceutical form	Sotagliflozin (SAR439954) will be supplied as 200 mg tablets	Sotagliflozin (SAR439954) will be supplied as 200 mg tablets	Placebo will be supplied as tablets (identical to sotagliflozin in appearance)
Dose, timing and route of administration	
Sotagliflozin 200 mg group:
 
One 200 mg tablet, taken orally once daily, before first meal of the day
 
One placebo tablet, taken orally once daily, before first meal of the day
	
Sotagliflozin 400 mg group:
 
Two 200 mg tablets, taken orally once daily, before first meal of the day
	
Placebo group:
 
Two placebo tablets, taken orally once daily, before first meal of the day

Duration of treatment	52 weeks following randomization		
Storage conditions	Store between +15°C and +30°C (59°F and 86°F)		

IMP = investigational medicinal product

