#### **11.4.3.2 Analyses of hypoglycemia**

The number (%) of patients and rate in patient years (2 types: the number of patients with events or the total number of events per 100 patient year) of all hypoglycemia events reported by the patient and confirmed by the Investigator, severe, and/or documented symptomatic hypoglycemia, will be summarized by treatment group respectively. Their pattern of occurrence over time will also be assessed, as appropriate.

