2.4.3.1 Extent of investigational medicinal product exposure

The extent of IMP exposure will be assessed by the duration of IMP exposure

Duration of IMP exposure is defined as last dose date of double-blind IMP – first dose date of double-blind IMP + 1 day, regardless of unplanned intermittent discontinuations (see [Section 2.5.3](#) for calculation in case of missing or incomplete data).

Duration of IMP exposure will be summarized descriptively as a quantitative variable (number, mean, SD, median, minimum, and maximum) during the 26-week core treatment period and 52-week entire treatment period, respectively. In addition, duration of treatment exposure will also be summarized categorically by numbers and percentages for each of the following categories and cumulatively according to these categories:

- 1 to 28 days,
- 29 to 56 days,
- 57 to 84 days,
- 85 to 126 days,
- 127 to 182 days,
- 183 to 364 days,
- >364 days

Additionally, the cumulative duration of treatment exposure will be provided, defined as the sum of the duration of treatment exposure for all patients, and will be expressed in patient years.

Number and percentages of patients with dose interruption/reduction due to creatinine increase (identified as those who answered Yes to the question “If Actual Total Daily Dose is 0, Was the dose interruption due to creatinine increase per protocol?” in e-CRF “Exposure” page) will be summarized.

Number and percentages of patients by final dose at the end of the treatment will also be presented by each treatment group.

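### SAP 2.4.5.1 calls patients with an event over total exposure an incidence rate; time after the first event stays in the denominator, so the figure is too low and depends on follow-up length

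*SAP*

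**What the plan says.** SAP 2.4.5.1 announces that "Two types of incidence rates will be presented". The first is patients with at least one event, "calculated as the number of patients with at least 1 event / total exposure in 100 patient-years". The second is all events, "calculated as the total number of events / total exposure in 100 patient-years". One note sets the denominator for both: "here exposure in days is duration of treatment-emergent AE period, ie, duration of IMP treatment in days +1". Nothing stops the clock at a patient's first event. SAP 2.4.3.1 gives the underlying duration: "Duration of IMP exposure is defined as last dose date of double-blind IMP – first dose date of double-blind IMP + 1 day".

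Protocol 11.4.3.2 names the same two rates ("the number of patients with events or the total number of events per 100 patient year") without saying how the patient-level denominator is formed.

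The measures cover any, severe and documented symptomatic hypoglycemia. Rates for severe or documented symptomatic events are repeated by sex, age, race and prior antidiabetic medication. SAP 2.4.5 asks for the 26-week and 52-week periods separately unless otherwise specified. SAP 2.4.5.1 also plans counts and percentages, a listing of all events, and a time-to-event display: "A KM curve will also be provided by treatment group for the time to first severe hypoglycemia or documented symptomatic hypoglycemia during the TEAE period". That curve is limited to the 52-week period. There is none for any hypoglycemia and none for 26 weeks.

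**The concern.** An incidence rate of first events divides first events by the time during which a first event could still occur. Here a patient who has an event in Week 3 goes on adding exposure to Week 52 but can add nothing more to the numerator. Three consequences follow.

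- **Level.** The printed figure is lower than the first-event rate, and the gap widens as events become more common.
- **Follow-up length.** Under a constant hazard the 26-week figure exceeds the 52-week figure, so the two summaries side by side suggest a decline that is only an artifact. Protocol 11.4.3.2 also wants the pattern of occurrence over time assessed.
- **Comparison.** With similar exposure, the arm with more events carries more time not at risk, so the ratio moves towards 1. The same holds across subgroups: with one common true ratio, the higher-risk subgroup prints the smaller ratio.

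Hypoglycemia is a named safety endpoint in a population in which any background antidiabetic therapy other than SGLT2 inhibitors is allowed, including insulin. These descriptive tables are where a reader will compare the arms.

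**Working it through.** The plan states no hypoglycemia rate, so there is no figure of its own to reproduce. The check compares the planned formula with first events over time at risk.

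**Inputs.** Planned treatment is "52 weeks following randomization" (Protocol Table 1). That is 364 days, plus 1 day under the SAP note, so T = 365/365.25 = 0.9993 years. The 26-week period is approximated as 183 days, T = 0.5010 years. Assumptions not taken from the documents: a constant first-event hazard λ, control-arm 52-week risks of 2% to 50%, true ratios of 1.5 and 2.0, and the dropout levels below.

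**Formulas, full follow-up.**
- Planned rate = (1 − e^(−λT))/T.
- Time-at-risk rate: expected first events are 1 − e^(−λT), and expected time at risk is (1 − e^(−λT))/λ. Their quotient is λ.
- For a true ratio of 2 and control risk p over the period, the planned ratio is [1 − (1 − p)²]/p = 2 − p.

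**Example, control risk 30%, true ratio 2.0.** λ = −ln(0.70)/0.9993 = 0.357 for control and 0.714 for active; the active risk is 1 − 0.70² = 0.51.
- Planned: 0.30/0.9993 and 0.51/0.9993, or 30.0 and 51.0 per 100 patient-years. Ratio 1.70, difference 21.0.
- Time at risk: 35.7 and 71.4. Ratio 2.00, difference 35.7.

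**Range of printed ratios.** The 26-week column uses the same hazards.

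| 52-week control risk | True 2.0, 52 weeks | True 2.0, 26 weeks | True 1.5, 52 weeks |
|---|---|---|---|
| 2% | 1.98 | 1.99 | 1.49 |
| 5% | 1.95 | 1.97 | 1.48 |
| 10% | 1.90 | 1.95 | 1.46 |
| 20% | 1.80 | 1.89 | 1.42 |
| 30% | 1.70 | 1.84 | 1.38 |
| 40% | 1.60 | 1.77 | 1.34 |
| 50% | 1.50 | 1.71 | 1.29 |

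The time-at-risk ratio is 2.00 or 1.50 in every row.

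**Dependence on follow-up.** For a hazard giving 50% risk at 52 weeks, λ = 0.6931/0.9993 = 0.694. The planned rate is (1 − e^(−0.694 × 0.5010))/0.5010, about 59 per 100 patient-years at 26 weeks, against 0.50/0.9993, about 50, at 52 weeks. The time-at-risk rate is 69.4 in both.

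**Unequal exposure.** With an independent dropout hazard d, patients with an event = [λ/(λ + d)](1 − e^(−(λ + d)T)), and total exposure = (1 − e^(−dT))/d.
- True ratio 2.0, dropout 10% control and 30% active: printed 1.73 at 30% control risk and 1.55 at 50%.
- True ratio 1.10, dropout 10% and 50%, 50% control risk: printed 1.11.
- Equal hazards, dropout 10% and 50%, 50% risk: patients with an event 0.477 and 0.375, a crude ratio of 0.79. The planned rates are 50.3 and 52.0, a ratio of 1.03.

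**The case against.** The strongest reply is that the planned measure answers a legitimate question. With equal follow-up its ratio is the 52-week risk ratio, which needs no constant-hazard assumption, whereas the first-event hazard does, and hazards are unlikely to be uniform when background therapy runs from none to insulin. The formula and exposure definition are printed, safety is descriptive, and no between-arm ratio of this rate is planned. The percentages, the rate of all events, the listing and the Kaplan-Meier curve stand beside it. Much of this is fair, and it limits the importance of the point. It does not justify the label, the low level on a per-patient-year scale, or 26-week and 52-week figures that differ under one hazard. The curve leaves out any hypoglycemia and the 26-week period.

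A reader might go further in three ways that the documents do not support.

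- That the rate adds nothing to the crude percentage. It adjusts in part for unequal exposure: in the equal-hazard case above it gives 1.03 where the percentages give 0.79.
- That it always shrinks differences. Shrinkage holds with similar exposure; a true 1.10 can print as 1.11 when dropout is very unequal.
- That it makes sotagliflozin look closer to placebo than it is. That presumes more hypoglycemia on the active arms, and neither document gives any rates.

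**Conclusion.** The point stands in a limited form. As defined, the patient-level figure is not a first-event incidence rate: it is too low, it depends on length of follow-up, and with similar exposure it moves ratios towards 1. If the true ratio is 2.0, the loss is 1% to 2.5% of the ratio at 2% to 5% control risk, which is negligible for severe hypoglycemia if it is that rare. It is 15% to 25% at 30% to 50% control risk, which would matter for any hypoglycemia if it is that common. Shrinkage is smaller at 26 weeks. These sizes rest on constant hazards and on assumed risks and dropout. The denominator problem itself follows from the SAP text alone. No efficacy analysis or formal test is affected.

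**What to change.** In SAP 2.4.5.1, define the patient-level rate as patients with at least one event of the category, divided by the sum of time from first dose to the first such event. For patients with no event, time runs to the end of the relevant treatment-emergent period: the earlier of EOT+1 and EOS for 52 weeks (the censoring rule already in SAP 2.5.4), and the 26-week treatment-emergent period defined in that section for 26 weeks. Apply this to every reported category, to both periods and to the subgroup tables. Use the same onset-date handling as the Kaplan-Meier analysis, and state it, because SAP 2.5.3 imputes partial onset dates only to classify events. Keep total exposure, with its note, for the rate of all events only.

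No new data are needed, since Protocol 10.6.1 collects onset date and time. The Protocol does not define the denominator, so the change does not contradict it. The cost is a separate denominator for each category and period, including any hypoglycemia and 26 weeks, for which the planned curve supplies nothing. If the present denominator is kept, the minimum is to relabel the measure as patients with events per 100 patient-years of total exposure.

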2.3.2 Safety population

Safety analyses will be based on the safety population, defined as all randomized patients who receive at least one dose of double-blind IMP (regardless of the amount of treatment administered), analyzed according to the treatment actually received.

In addition:

- Nonrandomized but treated patients will not be part of the safety population; however, their safety data will be presented separately
- Randomized patients for whom it is unclear whether they took the IMP will be included in the safety population as randomized
- When a patient is exposed to both sotagliflozin and placebo, the patient will be analyzed in the appropriate sotagliflozin group (depending on the treatment kits taken [400 mg or 200 mg])
- When a patient is exposed to both sotagliflozin 400 mg (treatment kits) and 200 mg (treatment kits), the patient will be analyzed in the sotagliflozin 200 mg group
- Randomized patients will be excluded from the safety population only if there is documented evidence (ie, all study dates recorded as no medication taken) that patients have not taken the study treatment. If a patient is dispensed double-blind IMP and is lost to follow-up without any documented evidence, the patient will be considered exposed.

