2.5.3 Missing data

For categorical variables, patients with missing data are not included in calculations of percentages unless otherwise specified. When relevant, the number of patients with missing data is presented.

Derived variables will be considered missing if any of the original variables required to calculate them are missing. For example, if either a baseline assessment or an endpoint assessment is missing for a particular patient, then change from baseline at endpoint will be missing. Depending upon the assessment, analyses may not include all patients in the analysis population, because certain patients in the intended population may have missing data.

Incomplete date of first administration of double-blind IMP

Date/time of first administration is the first non-missing start date/time of double-blind IMP completed in the e-CRF “First dose IMP” module.

For patients who are randomized and dispensed a double-blind treatment kit but who are lost to follow-up just after Visit 3 (eg. only the treatment kit number is reported in the e-CRF “Exposure - treatment period” module without any dose information), the date of first administration will be imputed using the date of randomization. When a patient is randomized but not exposed, “Not taken” should be ticked in the e-CRF “First dose IMP” module.

Handling of computation of treatment duration if investigational medicinal product end of treatment date is missing.

For the calculation of the treatment duration, the date of the last dose of IMP is equal to the date of last administration reported on the on the e-CRF “Treatment status library” page. If this date is missing, the exposure duration should be left as missing.

The last dose intake should be clearly identified in the case report form and should not be approximated by the last returned package date.

Handling of medication missing/partial dates

No imputation of medication start/end dates or times will be performed. If a medication date or time is missing or partially missing and it cannot be determined whether it was taken prior or concomitantly, it will be considered a prior, concomitant, and posttreatment medication.

Handling of adverse events/hypoglycemia with missing or partial date/time of onset

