Missing or partial adverse event onset dates and times will be imputed so that if the partial adverse event onset date/time information does not indicate that the adverse event started prior to treatment or after the treatment-emergent adverse event period, the adverse event will be classified as treatment-emergent. No imputation of adverse event end dates/times will be performed. These data imputations are for categorization purpose only and will not be used in listings. No imputation is planned for date/time of adverse event resolution.

Handling of adverse events/hypoglycemia when date and time of first investigational medicinal product administration is missing

When the date and time of the first IMP administration is missing, the day of randomization should be considered as the start date of TEAE period (see Section 2.1.4). The exposure duration should be kept as missing.

Handling of adverse events/hypoglycemia when IMP end of treatment date is missing

For the purpose of defining TEAE period, the date of the last administration of double-blind IMP is equal to the date of the last administration reported on the e-CRF "Treatment Status Library" page.

If the date of last administration reported on the e-CRF "Treatment Status Library" page is

- Partially missing, it will be imputed with a date as late as possible before or on the date of last available information on e-CRF "Completion of End of Study/Follow-up".
- Completely missing, it will be imputed with the date of last available information on e-CRF "Completion of End of Study/Follow-up" page.

If the date of last available information on e-CRF "Completion of End of Study/Follow-up" page is:

- Partially missing, it will be imputed with a date as late as possible.

Completely missing, all adverse events occurred on or after the first administration of double-blind IMP will be considered as treatment emergent adverse events.

Handling of missing assessment of relationship of adverse events to IMP

If the assessment of the relationship to IMP is missing, then the relationship to IMP has to be assumed and the adverse event considered as such in the frequency tables of possibly related adverse events, but no imputation should be done at the data level.

Handling of missing severity/grades of adverse events

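### Hypoglycaemia rates: when a dose date is missing, SAP 2.5.3 imputes it for counting events but leaves the exposure missing, so numerator and denominator can cover different patients

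*SAP*

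**What the plan says.** **Event window.** SAP 2.4.5.1 states that "Analyses of hypoglycemia will be performed on the TEAE period as defined in Section 2.1.4". For hypoglycaemia that window runs from first dose to one day after last dose (SAP 2.1.4).

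**Rates.** Two rates per 100 patient-years are planned, one for patients with at least one event and one for events. The second is "calculated as the total number of events / total exposure in 100 patient-years", and the first uses the same denominator. A note defines that denominator: "here exposure in days is duration of treatment-emergent AE period, ie, duration of IMP treatment in days +1".

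**Missing dates, for the window.** SAP 2.5.3, under headings that name hypoglycaemia, imputes the missing boundary:
- First dose missing: "the day of randomization should be considered as the start date of TEAE period".
- Last dose partly missing: set as late as possible, up to the last date on the end-of-study page.
- Last dose wholly missing: "Completely missing, it will be imputed with the date of last available information on e-CRF" for the end of study. If that date is wholly missing too, every event from first dose onward counts as treatment-emergent.

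**Missing dates, for the duration.** The same section says of a missing last-dose date: "If this date is missing, the exposure duration should be left as missing". Directly after the first-dose window rule it says: "The exposure duration should be kept as missing".

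**Population.** These patients stay in the safety population. SAP 2.3.2 says: "If a patient is dispensed double-blind IMP and is lost to follow-up without any documented evidence, the patient will be considered exposed".

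**The concern.** A rate is interpretable only if events and person-time come from the same patients over the same period. Here one set of rules keeps a patient's events when a dose date is missing, and another removes that patient's time. No rule found in the SAP takes the events out or puts the time back.

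The resulting error has one direction: the rate is too high. Severe hypoglycaemia is an event of special interest (SAP 2.1.4.2), and readers will compare these rates across arms. If the arms lose different amounts of person-time in this way, the rates will differ without any difference in risk.

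**Working it through.** **Step 1. The two halves of the denominator note.**

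| Situation | Length of event window | IMP duration + 1 |
|---|---|---|
| Both dates known | last − first + 1, plus 1 day | the same |
| First dose missing | runs from randomization | missing, stated explicitly |
| Last dose wholly missing | runs to the imputed end date | missing, by the treatment-duration rule |

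The halves agree in the first row only. In the second row the leave-missing instruction stands beside the window rule under a hypoglycaemia heading, so the mismatch is explicit. In the third row it depends on which half is programmed. For a partly missing last-dose date the duration rule is silent on whether partial counts as missing.

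One rule cuts across this: SAP 2.5.3 also imputes the first-dose date as the randomization date for patients lost just after Visit 3 with only a kit number recorded. Their last-dose date would normally be missing too, so they would still add no time.

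**Step 2. Formulas.** Let E₀ and T₀ be events and time from patients with a duration, and E₁ and T₁ the same for patients without one.
- As written: (E₀ + E₁)/T₀
- Matched: (E₀ + E₁)/(T₀ + T₁)
- Both excluded: E₀/T₀

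As written over matched = 1 + T₁/T₀, which exceeds 1 whenever T₁ > 0 and the arm has an event. As written over both excluded = 1 + E₁/E₀, which exceeds 1 only if an affected patient had an event. With equal true rates the two ratios agree in expectation. If s is the share of the arm's person-time left out, the factor is 1/(1 − s).

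**Step 3. Arm size.** The documents state no hypoglycaemia rate and no frequency of missing dates. The one stated figure of use is 92 patients per arm (SAP 1.3). It reproduces: n = 2(1.960 + 0.842)² × 1.2²/0.5² = 90.4, so 91 per arm. Power at 92 is 0.807 by the normal approximation and 0.803 by the t distribution.

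**Step 4. Size.** Assumptions: m affected patients of 92 (range 0 to 9); d true treatment days each (range 7 to 364); 365 days for everyone else (364 + 1). Factor = 1 + m(d + 1)/[(92 − m) × 365].

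| m | d = 7 | d = 182 | d = 364 |
|---|---|---|---|
| 1 | 1.000 | 1.006 | 1.011 |
| 2 | 1.000 | 1.011 | 1.022 |
| 3 | 1.001 | 1.017 | 1.034 |
| 5 | 1.001 | 1.029 | 1.057 |
| 9 | 1.002 | 1.054 | 1.108 |

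Example: m = 9, d = 364 gives 92/83 = 1.108.

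**Step 5. Between arms, equal true rates.** At full exposure, 5 versus 1 affected patients gives (92/87)/(92/91) = 1.046, and 9 versus 2 gives (92/83)/(92/90) = 1.084. Time matters, not headcount: 5 patients with 7 days each give 1.001, while 2 patients with 364 days each give 1.022.

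**The case against.** **The note can be read as already correct.** It names the treatment-emergent period first, and the last-dose imputation is given for the purpose of defining that period. The leave-missing rule for the last dose sits under a heading on treatment duration, which is the quantity in SAP 2.4.3.1, and 2.4.5.1 does not cite it. This stands in part: for a missing last dose the text is ambiguous rather than plainly wrong. It does not rescue the missing-first-dose case, and the equation with IMP duration plus one day points the other way.

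**The effect is likely to be tiny.** The patients the SAP describes are those lost early, for whom little time is at stake. Protocol 10.2.1 and 10.3.4 require dosing dates and permanent discontinuations to be recorded, and SAP 2.5.3 asks that the last dose be clearly identified. This stands; missing dates may be few.

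**Little rests on these rates.** Safety analyses are descriptive (SAP 2.4.5) and no between-arm rate ratio is specified. The percentage of patients with hypoglycaemia does not use this denominator. The Kaplan-Meier analysis substitutes the end-of-study date for a missing end-of-treatment date (SAP 2.5.4). All of this stands, although the last point also shows that the SAP retains time in one hypoglycaemia analysis that it may drop in another.

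**Imputing exposure has its own cost.** Patients who stop treatment are asked to remain in the study (Protocol 10.3.4), so an end-of-study date can bring off-drug time and events into an on-treatment rate. This stands, and the fix should allow for it.

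**Conclusion.** The inconsistency is real: explicit for a missing first-dose date, ambiguous for a missing last-dose date. Where a patient contributes an event but no time, the rate is biased upward, by an amount set by the share of the arm's person-time left out. Over the assumed range of 0 to 9 of 92 patients, that is about 0% to 11% per arm. The upper end needs nine patients with no recorded duration but a full year of treatment. The effect is probably small.

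A reader might infer three stronger things that the documents do not support:
- That the arm with the most affected patients will look worst. That follows only if affected patients have similar treatment time in each arm.
- That every missing date inflates the rate. Compared with leaving the patient out altogether, one without an event changes nothing.
- That a spurious ratio of 1.05 to 1.08 is to be expected. Those values rest on assumed counts and full follow-up, and the documents give no frequency of missing dates.

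This deserves a clarifying sentence before the final analysis. It is not a reason to distrust the other hypoglycaemia summaries.

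**What to change.** In SAP 2.4.5.1, state that exposure for the hypoglycaemia rates is computed from the same start and end dates that define the treatment-emergent period, including dates imputed under 2.5.3. Where no end-of-study date exists, use the last contact date, as the censoring note in 2.5.4 already does.

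Add two items:
- the number of patients with an imputed first- or last-dose date, by arm;
- a sensitivity rate that excludes these patients from both numerator and denominator, because imputing to the end of study can add off-drug time and events.

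Keep the leave-missing rule for the descriptive exposure table only, and say there whether a partly missing last-dose date counts as missing.

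The cost is one sentence in 2.4.5.1, a clarification in 2.5.3, one count and one extra set of rates. No new data are needed.
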